# **Vitamin D as an Intervention for Improving Quadriceps Muscle Strength in Patients after Anterior Cruciate Ligament Reconstruction: A Randomized Double-Blinded, Placebo-Controlled Clinical Trial**

## **Background**

In Hong Kong, over 3000 Anterior Cruciate Ligament reconstructions (ACLR) are performed each year in order to restore the knee function after an ACL injury. The goal of the ACLR especially for athletes is to return to sports and recondition the athlete back to the preinjury level of sport. Despite a successful surgery and a strenuous rehabilitation process, some athletes still fail to qualify the Return-To-Play (RTP) criteria, and 23% among those who returned to high-risk sport would suffer a second ACL injury (1).

After ACLR, the patient would undergo post-operative rehabilitation to strengthen muscle groups associated to the knee. In the beginning of phase one (0-4 weeks post-surgery), controlled mobilization is required for the protection of the ACL graft and the reduction of swelling. Then, phase 2 (5 - 9 weeks post-surgery) consists of controlled rehabilitative training while phase 3 (10-16 weeks post-surgery) involves intensive muscle strengthening and training. During phase 4 (17-26 weeks post-surgery), patients would undergo advanced agility and endurance training. Finally, phase 5 (26 weeks post-surgery onwards) aims to prepare patients for a gradual return to sports. Most of the patients would be expected to RTP by 12 months. Despite the comprehensive rehabilitation program, a systematic review showed that up to 35% of patients would fail to return to their preinjury level of sport (2).

Quadriceps muscle weakness after ACLR is a major limiting factor for functional recovery. It is contributed by arthrogenic muscle inhibition and muscle atrophy, which are resulted from muscle disuse, joint swelling, pain, inflammation and damage of neuroreceptors in the joint after the surgery. Muscle size is a determinant of muscle strength. Postoperative quadriceps muscle atrophy is inevitable, but muscle strength should be regained through rehabilitation. As the patient continues to exercise during rehabilitation, the atrophic response subsides and the strengthening training stimulates significant hypertrophy in quadriceps muscle, and thus increasing the quadriceps strength (3). However, in some patients, this hypertrophic response is insufficient and can lead to persistent quadriceps muscle atrophy after ACLR.

This study would benefit patients who suffered from persistent quadriceps weakness and atrophy after ACLR, thus improving the post-operative outcome. This would lead to a better RTP rate as well as reducing the risk of reinjury, which can be a burden to the health system and the society due to the additional treatments and extended time off-work.

## **Objectives**

1. To determine the correlation between vitamin D status and quadriceps muscle strength at pre-op and at 4 months after ACLR.
2. To conduct a randomized-controlled trial to examine the therapeutic effects of vitamin D supplement on improving vitamin D deficiency status in patients with quadriceps muscle weakness after ACLR.
3. To examine the effect of vitamin D supplements on the quadriceps muscle strength for patients after ACLR.

## Hypothesis

1. Vitamin D supplements will improve the vitamin D status of patients with vitamin D  $<20\text{ng/ml}$  and quadriceps muscle weakness after ACLR
2. The improved level of vitamin D will lead to an improvement in quadriceps muscle strength and size.

## Patient Recruitment & Eligibility

This is a prospective randomized, double-blinded placebo-controlled trial with all participants being recruited at the out-patient clinic of Prince of Wales Hospital. Participants are randomly assigned into either the Vitamin D intervention group or the placebo-controlled group through an online computer generator sequence at the time of admission to the out-patient clinic. 60 participants will be recruited, with 30 in each group. The study will be carried out in compliance with Declaration of Helsinki and the ICH-GCP. Ethical approval will be obtained from the local IRB before the study starts. Informed consent must be obtained from all patients in order to participate in the study.

Participants will be recruited according to the following criteria:

Inclusion Criteria	Exclusion Criteria

1) Aged 18-40 with unilateral ACL injury

2) Sporting injury with a Tegner score of 7

3) Pre-op serum vitamin D level <math><20\text{ng/ml}</math>

4) 4 months post-ACLR with serum Vitamin D level remained <math><20\text{ng/ml}</math>

5) LSI for quadriceps strength <math><70\%</math> of contralateral leg at 4-month isokinetic assessment

6) Both knees without history of injury/prior surgery

	

1) Concomitant bone fracture, major meniscus injury or full-thickness chondral injuries requiring altered rehabilitation program post-operatively

2) Pre-operative radiographic signs of arthritis

3) Metal implants that would cause interference on MRI

4) Non-HS graft for ACLR

5) Patient non-compliant to the rehabilitation program

6) Regular sunbed users

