## **Sample Size Estimation and Power Calculation**

For objective 1, when the sample size is 92, a bivariate correlation test will have 90% power to detect at the 0.050 level with a correlation coefficient of 0.3. The proposed sample size (150) will be sufficient to detect the difference and enables the fulfillment of objective 2 and 3 in this study (with an estimated 40% quadriceps strength deficit at 4-month post-op). For objective 2, when the sample size in each group is 30, a repeated-measure ANOVA (with three repeated measures) will have 90% power to detect at the 0.050 level, with an effect size of 0.35. (G\*Power 3.1.9.4).

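### The single recruitment list and its 60 participants cannot be reconciled with objective 1, which is powered at 92 with 150 proposed; followed as written, the correlation loses its stated 90% power

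*Protocol*

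**What the plan says.** Objectives, item 1: "To determine the correlation between vitamin D status and quadriceps muscle strength at pre-op and at 4 months after ACLR".

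Patient Recruitment & Eligibility describes the randomised trial, gives the number as "60 participants will be recruited, with 30 in each group", and then states "Participants will be recruited according to the following criteria". One list follows. Inclusion 3 and 4 require vitamin D below 20 ng/ml pre-op and again at 4 months. Inclusion 5 requires an LSI below 70% at the 4-month isokinetic test. Nothing limits any item to the randomised stage.

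Sample Size Estimation and Power Calculation uses other numbers. Its premise is "For objective 1, when the sample size is 92", based on r = 0.3, alpha 0.05 and 90% power. It then claims "The proposed sample size (150) will be sufficient to detect the difference and enables the fulfillment of objective 2 and 3 in this study", and qualifies this in brackets by "with an estimated 40% quadriceps strength deficit at 4-month post-op". The randomised comparison is sized separately at 30 per group.

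Data Processing and Analysis assigns objective 1 a Pearson correlation at 4 months. It mentions no wider cohort and no allowance for restricted range.

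**The concern.** Sixty is below both 92 and 150, and the Protocol gives the remaining people no entry criteria and no visits. A site that applies the list literally has no stated basis for following a patient who fails the vitamin D or LSI limits.

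The list also selects on the variables that objective 1 relates. At 4 months it removes everyone with sufficient vitamin D and everyone with a good LSI, and selecting low values of both variables weakens their correlation. At the pre-op time point vitamin D is truncated. Strength is not directly truncated there, but the people analysed would have been chosen on results obtained four months later.

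At stake is whether objective 1 can be answered with the stated power. Eligibility and enrolment number belong in the Protocol, and no later analysis plan can recover patients who were never followed.

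**Working it through.** **Inputs from the Protocol.** r = 0.3, alpha 0.05 (sidedness not stated), 90% power, n = 92, proposed n = 150, 40% strength deficit at 4 months, 60 recruited, and the cut-offs in inclusion 3–5.

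**1. Reproduce the 92.** Fisher z: N = ((z_alpha + z_power) / atanh r)² + 3, with atanh 0.3 = 0.3095.
- One-sided: ((1.645 + 1.282) / 0.3095)² + 3 = 92.4. The exact distribution of r gives 92.
- Two-sided: ((1.960 + 1.282) / 0.3095)² + 3 = 112.7. The exact figure is 112.

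So 92 reproduces as a one-sided calculation. A two-sided test with 92 has 83.6% power. Both versions are shown below.

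**2. Link the 150 and the 60.** 150 × 0.40 = 60. This suggests a wider cohort feeding the trial, though the Protocol does not say so.

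**3. Effect of n = 60 alone, with r still 0.3.** Power ≈ Φ(atanh r × √(n − 3) − z_alpha).
- 0.3095 × √57 = 2.337.
- One-sided: Φ(2.337 − 1.645) = 0.756 (exact 76.3%).
- Two-sided: Φ(2.337 − 1.960) = 0.647 (exact 65.4%).
- For comparison, 150 unselected people give 98.3% one-sided and 96.4% two-sided (exact).

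This step uses only the Protocol's figures.

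**4. Effect of truncation.** The Protocol does not give the share of patients below each cut-off, so these are assumptions: 30–90% below 20 ng/ml and 40–90% below LSI 70%. Further assumptions are joint normality, LSI standing in for strength, and a true r of 0.3. For the columns with all three cut-offs, the pre-op and 4-month vitamin D values correlate 0.6–0.8, and pre-op vitamin D relates to LSI only through the 4-month value. Simulation used 2 million draws. Power is for n = 60, one-sided / two-sided.

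| Below vitamin D cut-off | Below LSI cut-off | r, 4-month cut-offs only | Power | r, all three cut-offs | Power |
|---|---|---|---|---|---|
| 30% | 40% | 0.115 | 22% / 14% | 0.119–0.123 | 23–24% / 15% |
| 60% | 40% | 0.135 | 27% / 18% | 0.136–0.139 | 27–28% / 18% |
| 90% | 90% | 0.229 | 55% / 42% | 0.226–0.227 | 54% / 41–42% |

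Taking the lower one-sided figure in the first and last rows, r is about 0.12–0.23 and power about 22–54% one-sided (14–42% two-sided).

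**5. Would 150 people who all met the list be enough?** In the 60% / 40% case, power is about 50% one-sided (38% two-sided). In the mildest case, 90% / 90%, it is about 88% one-sided (81% two-sided). Neither reaches 90%.

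**The case against.** The strongest reply is that the list was meant only for those randomised. The eligibility section opens by describing a randomised placebo-controlled trial with 30 per group, the sample size section treats objectives 1 and 2 separately, and 150 × 40% = 60 ties them together. On that reading nothing is truncated and 150 people give ample power. This is probably the intention. It stands as a reason to treat the defect as one of definition, but it does not remove it: the Protocol neither limits the list to the randomised part nor says who else enters.

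The size of the attenuation is also open to challenge. The shares are not in the Protocol, and LSI is a between-leg ratio whereas objective 1 says strength. If strength means torque correlated 0.5–0.7 with LSI (again an assumption), r would be about 0.15–0.21 and two-sided power at n = 60 about 20–36%. Power remains low, but no narrow range is secure. The loss from n = 60 alone does not depend on any of this.

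A reader might also infer that patients are turned away at the first blood test, so that no 4-month data could exist. The Protocol gives no screening sequence, and its Biochemical Assays section has samples frozen until analysis, so this does not follow.

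**Conclusion.** The concern holds as a contradiction between the recruitment section and the sample size section. Followed as written, objective 1 has about 76% power one-sided (65% two-sided) instead of 90%, from sample size alone. Truncation lowers it further, to about 22–54% one-sided (14–42% two-sided) under the assumed shares.

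Three stronger readings are not supported:
- That objective 1 needs 150 people across the whole range. The calculation needs 92; 150 is the proposed size, and a full range is only inferred from the 150-to-60 arithmetic.
- That a null correlation would be an artefact of the list. That depends on the list actually being applied to the objective 1 sample, which was probably not intended.
- That the randomised comparison is damaged. Quadriceps strength is its primary outcome, it is sized at 30 per group, and this point does not touch it.

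The correction should be made before recruitment, but the point concerns a correlational objective and not the trial's main comparison.

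**What to change.** Reconcile the two sections in the Protocol:
- State that inclusion 3, 4 and 5 and the number 60 apply to the randomised part only.
- Define the objective 1 cohort, the 150 already proposed, by inclusion 1, 2 and 6 and the exclusions, with no vitamin D or LSI limit.
- State that failing inclusion 3–5 ends eligibility for randomisation only, and that the objective 1 correlation uses the whole cohort.
- Schedule serum vitamin D and strength at both times that objective 1 names.

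Do not state that the 150 will supply the 60. With 30–70% below the vitamin D cut-off, 40–60% below the LSI cut-off and a pre-op to 4-month vitamin D correlation of 0.6–0.8 (all assumed), about 9–41% would meet inclusion 3–5. That is roughly 14–61 of 150, before refusals. Yield is a separate question.

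Cost: Protocol wording and consent covering the cohort stage. Patients who fail inclusion 3–5 must still attend the 4-month blood and strength tests. Pre-op strength testing, which objective 1 implies but the Protocol does not schedule, must be done across the cohort.

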## Method

### Intervention

For the proposed study, we will use 2000IU/day as advised by the Endocrine Society (4). Previous study has shown 2000 IU/day for 4 months showed significant improvement of muscle strength (5). Therefore, for the proposed study, we will use 2000 IU/day (a standard formulary used in Hospital Authority in our cluster), for a duration of 16 weeks.

Subjects will be randomized into 2 study groups:

Group 1: Placebo group

Group 2: Intervention group - patients receive daily dose of 2000 IU of vitamin D3 supplements

All study tablets including the placebo will be manufactured according to Good Manufacturing Practice (GMP) guidelines for quality assurance. They will be taken with water at breakfast, 2 tablets at a time and once daily. The treatment will last for 16 weeks after which the supplementation will be stopped. Subjects will continue with their usual lifestyles in diet and physical activity without receiving any other treatment for muscle health. The procurement of study tablets will be covered by departmental funding.

### Outcome Measurements

#### 1. Anthropometric Measurement

Body Mass Index (BMI) would be calculated by the measured height and weight at 4 months post ACLR before vitamin D supplements, during the eighth week of vitamin D supplements, after the completion of 16 weeks vitamin D supplements, and 12-months post-operation. We would measure the waist circumference as well. Subcutaneous fat would be measured using skinfold techniques for the triceps brachii and biceps brachii.

#### 2. Biochemical Assays

Blood samples will be taken under non-fasting conditions. Serum / plasma obtained will be immediately stored at -80°C until analysis. Serum 25(OH) Vit-D assay: Serum 25(OH)Vit-D levels will be measured by commercial 25(OH) Vitamin D ELISA kit (Abcam ab213966) according to the manufacturer's instruction, providing the quantitative determination of 25(OH) Vitamin D3 and 25(OH) Vitamin D2. Sensitivity: 1.98 ng/ml (Range: 0.5 ng/ml - 1010 ng/ml).

#### 3. Radiological Assessment

##### (a) Magnetic Resonance Imaging (MRI)

Muscle volumes of quadricep muscle are measured using a 1.5 or 3.0 Tesla MRI Scanner. Axial (3mm thick cut) T1W images are obtained from the anterior superior iliac supine (ASIS) to patella. Quadriceps muscles were manually outlined in each axial slice. Muscle volume was calculated by summing all of the slice-multiplied by slice thickness. The quality of the muscle is assessed by analyzing the fat content of the muscle mass using technique that has been reported by Reeder et al (6). Bilateral legs will be performed before the start of the vitamin supplementation (4 months post-op) and with the injured side repeated after the completion of the 16-weeks supplementation (8 months postop).The uninjured side will be used as reference for 'normal volume'.

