## **Data Processing and Analysis**

Data will be reported as the mean  $\pm$  standard error of the mean, except for non-normally distributed data which are reported as the median, minimum and maximum. All Statistical analysis will be performed using the Statistical Package for Social Sciences (SPSS) 25. Statistical significance will be set at  $p < 0.05$ . For objective 1, a bivariate Pearson's correlation will be used to detect correlation between serum vitamin D levels and muscle strength and size at 4-month post-op, controlled for anthropometric variables. For objective 2, data will be analyzed by a repeated-measure ANCOVA (Control vs vitD supplementation; with repeated measures at 4-, 8-, 12-month post-op; other anthropometric variables as covariance). Primary outcome would be quadriceps muscle strength. These statistical tests will be performed after checking the normal distribution with Kolmogorov-Smirnov test, otherwise, a non-parametric

equivalent will be used. The “Intention-to-Treat” principle will be followed for data analysis purposes on those who have completed 16-week treatment. “Protocol Evaluable Analysis” will also be conducted using the 80% compliance as the cut-off. This trial will be registered at a clinical trial registry ([ClinicalTrials.gov](https://www.clinicaltrials.gov)) before the study is implemented.

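### The 90% power given for objective 1 does not carry over to the muscle-size correlation, because a 4-month MRI is assured only for the 60 or fewer trial participants, who are selected on vitamin D and strength

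*Protocol*

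**What the plan says.** - **Objectives.** Objective 1 correlates vitamin D status with quadriceps muscle strength. It does not name muscle size.
- **Data Processing and Analysis.** The objective 1 analysis is wider. It is to detect "correlation between serum vitamin D levels and muscle strength and size at 4-month post-op".
- **Outcome Measurements, 3(a) Magnetic Resonance Imaging (MRI).** This is the only source of muscle size. The first scan is scheduled thus: "Bilateral legs will be performed before the start of the vitamin supplementation (4 months post-op". The injured side is scanned again after the 16 weeks of supplementation. The section does not say whether anyone outside the randomized trial is scanned.
- **Sample Size Estimation and Power Calculation.** "For objective 1, when the sample size is 92", it says, "a bivariate correlation test will have 90% power to detect at the 0.050 level with a correlation coefficient of 0.3". It adds that "The proposed sample size (150) will be sufficient to detect the difference" and that this number also serves objectives 2 and 3, given an estimated 40% strength deficit at 4 months. It does not say which muscle outcome the correlation of 0.3 refers to, or whether the test is one- or two-sided.
- **Patient Recruitment & Eligibility.** "60 participants will be recruited, with 30 in each group". These patients must have vitamin D below 20 ng/ml before surgery and again at 4 months, and a quadriceps LSI below 70% at 4 months. No cohort of 150 is described there.

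**The concern.** The analysis section puts size beside strength under objective 1, so a reader will take the 90% power to cover both. The two outcomes do not have the same data behind them. The 4-month vitamin D level and isokinetic test are needed to decide eligibility, so they can exist for patients who are never randomized. The MRI is timed by the start of treatment, and only randomized patients start treatment.

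The scanned patients are also a selected group. Eligibility removes the upper part of the vitamin D range directly. It restricts size indirectly, through strength; the Background section itself calls muscle size a determinant of strength. Restricting the range in this way lowers the correlation itself, on top of the smaller sample.

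At stake is the reading of a null result. A non-significant size correlation would be reported under an objective with 90% stated power and taken as evidence of no association, when the design had limited ability to show one.

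**Working it through.** **Inputs from the Protocol:** r = 0.3, alpha 0.05, power 90%, n = 92, cohort 150, estimated deficit 40%, randomized 60. If the 40% is read as a share of patients, 150 × 0.40 = 60, which matches the randomized number.

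**Step 1. Reproduce the stated n.** Fisher z: n = ((z_alpha + z_power) / atanh(r))² + 3, with atanh(0.3) = 0.3095.
- One-sided: ((1.645 + 1.282) / 0.3095)² + 3 = 92.4. This reproduces 92.
- Two-sided: ((1.960 + 1.282) / 0.3095)² + 3 = 112.7, so 113. This does not reproduce 92, and 92 patients would have 83% power.

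Both bases are carried below so that each is compared like for like.

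**Step 2. Size correlation at n = 60, no truncation.** Power = Φ(atanh(r) × √(n − 3) − z_alpha), and 0.3095 × √57 = 2.337.
- One-sided: Φ(2.337 − 1.645) = Φ(0.692) = 76%.
- Two-sided: Φ(2.337 − 1.960) = Φ(0.377) = 65%.

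Simulating the t test of r gave the same rounded values. This step uses only the Protocol's own figures, once the scanned group is taken as 60.

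**Step 3. Strength correlation at n = 150.** 0.3095 × √147 = 3.753.
- One-sided: Φ(3.753 − 1.645) = 98%.
- Two-sided: Φ(3.753 − 1.960) = 96%.

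**Step 4. Truncation on vitamin D only (assumed).** Let f be the share of the cohort below 20 ng/ml, c the normal quantile of f, λ = φ(c)/f, and v = 1 − cλ − λ². Then r′ = 0.3√v / √(1 − 0.09 + 0.09v).
- f = 80%: r′ = 0.23; power at n = 60 is 56% one-sided, 43% two-sided.
- f = 40%: r′ = 0.17; power 37% one-sided, 26% two-sided.

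**Step 5. Truncation on vitamin D and LSI (assumed).** Trivariate normal simulation. Vitamin D correlates 0.3 with size and 0.3 with LSI, the lowest 40% of LSI is kept, and the size–LSI correlation is 0.3 or 0.7. Power is by the Step 2 formula at n = 60.

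| Vitamin D share kept | Size–LSI correlation | Restricted r | One-sided | Two-sided |
|---|---|---|---|---|
| 80% | 0.3 | 0.21 | 49–50% | 37% |
| 80% | 0.7 | 0.17 | 36% | 25% |
| 40% | 0.3 | 0.16 | 34% | 23% |
| 40% | 0.7 | 0.13 | 25–26% | 16–17% |
| 30% | 0.3 | 0.15 | 30% | 20% |
| 30% | 0.7 | 0.12 | 23–24% | 15% |

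The Protocol gives neither the vitamin D distribution nor the size–LSI and vitamin D–LSI correlations, so Steps 4 and 5 show a range, not an estimate. Ranges such as 49–50% cover rounding of r and simulation error.

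**The case against.** The strongest defence has four parts.

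1. **Objective 1 is about strength.** A reader might infer that the power of objective 1 as a whole fails. The documents do not support that. The Objectives section names strength only, and strength keeps 96 to 98% power in 150 patients. This part stands: the shortfall belongs to the size correlation added in the analysis section, for which no separate power is given.

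2. **The MRI section gives a time, not a population.** A reader might infer that scans are limited to 60. The text does not say so; it leaves open whether the rest of the 150 are scanned. This also stands, as a limit on the claim. What can be said is that no section provides a scan for anyone who does not start supplementation, so size data are assured only for trial participants.

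3. **The cohort of 150 is planned.** Because the recruitment section describes only 60, a reader might infer that the strength correlation is also confined to the truncated group. The sample size section points the other way: it proposes 150 for objective 1, and its 40% figure yields the 60 randomized. The two sections need reconciling, but the silence of one does not cancel the number in the other.

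4. **The loss from truncation can be overstated.** Cutting size itself at the eligibility limits, as if size and LSI were one variable, gives r of about 0.11 to 0.16 and two-sided power of 14 to 24%. Eligibility cuts LSI, a side-to-side strength ratio, not muscle volume, so that calculation is the pessimistic end. Setting a two-sided result against the stated 90%, which reproduces only one-sided, would also exaggerate the gap.

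None of this restores 90% power for size in 60 patients. Power falls short on either basis, with or without truncation.

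**Conclusion.** The point holds for muscle size only. The Protocol puts size under an objective powered on 92 patients, with 150 proposed, but assures the measurement for 60 or fewer, selected on vitamin D and on LSI. If the size correlation rests on those 60, power is 76% one-sided or 65% two-sided at r = 0.3 before truncation. This rests on the Protocol's own inputs and on reading the MRI schedule as covering trial participants only.

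With the lowest 30 to 80% of vitamin D and the lowest 40% of LSI kept, a size–LSI correlation of 0.3 to 0.7 and a vitamin D–LSI correlation of 0.3, r falls to about 0.12 to 0.21. Power is then about 23 to 50% one-sided or 15 to 37% two-sided. These figures are conditional on assumptions that the Protocol neither states nor contradicts.

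The strength correlation is sound if it is run in the 150. The randomized comparison and its primary outcome are not touched. The change should be made, because it corrects a power claim that the design does not deliver for one of the two outcomes listed under objective 1.

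**What to change.** - **Data Processing and Analysis:** state that the objective 1 strength correlation uses all patients in the cohort of 150 who have a 4-month vitamin D and isokinetic result, before the vitamin D and LSI inclusion criteria are applied.
- **Patient Recruitment & Eligibility:** reconcile with the sample size section by describing the cohort of 150 as well as the 60 randomized from it.
- **Muscle size:** remove it from objective 1, in line with the Objectives section. Otherwise label it exploratory in the MRI subset (n at most 60, range-restricted), state its own lower power, and say that a null result will not be read as no association.
- **MRI section:** state who receives the 4-month scan.
- **Sample Size Estimation and Power Calculation:** state that the figure of 92 is one-sided, or restate it two-sided (113), and say that it applies to strength.

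**Cost:** mainly wording and restated figures, with no extra scans. The size correlation loses its confirmatory standing. The 4-month blood and isokinetic tests must also be kept for patients who fail the pre-operative vitamin D criterion. The Protocol does not confirm that they are done, so the sponsor should check this before relying on the full 150.
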